5.1 Subject Grouping

Subjects will be grouped according to the actual treatment they received. Subjects with the same dose level from the dose escalation and exploratory in Phase 1a for monotherapy and Phase 1a for combination will be combined for summary.

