**Table 5: Anticipated Dose Levels**

Design	Dose	Regimen
Accelerated titration design	0.07 mg FPT155	Q3W
	0.21 mg FPT155	Q3W
	0.70 mg FPT155	Q3W
	2.1 mg FPT155	Q3W
3+3 design	7 mg FPT155	Q3W
	21 mg FPT155	Q3W
	42 mg FPT155	Q3W
	70 mg FPT155	Q3W
	140 mg FPT155	Q3W
	280 mg FPT155	Q3W
	560 mg FPT155	Q3W
	840 mg FPT155	Q3W
	1260 mg FPT155	Q3W

Abbreviations: Q3W = once every 3 weeks.

Planned dosing increments take into account conservative estimates of RO and PA through both CD28 and CTLA-4. Fixed 3-fold escalation increments are proposed while projected engagement of CD28 is low; more conservative increments (2-fold or less) are proposed at higher CD28 occupancy levels.

The Sponsor may add cohorts with alternative dose levels or dose regimens (e.g., different dosing frequency, intermediate dose levels) upon review of safety, PK, and PD profiles to achieve optimal target exposure with acceptable tolerability. The dose level of 700mg was replaced by 840mg based on preliminary PK showing dose-proportional increases in exposure and approximately 30-50% interpatient variability in exposure at a given dose level – the range of exposures from FPT155 560mg and from FPT155 700mg (25% increase in dose) were predicted not to be significantly different. A 1.5-fold increment in dose levels has been selected

above 560mg based on early safety results showing an absence of DLTs or cytokine release syndrome through the 560mg dose level with the presence of immune-related toxicity manageable with standard of care treatment for irAEs. Following clearance of a dose at the Q3W schedule, more frequent (eg Q2W) dosing at the same dose level may be evaluated using the 3+3 framework.

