#### 4.1.3 Phase 1b FPT155 Monotherapy Dose Expansion

Enrollment in Phase 1b dose expansion will begin when the MTD and/or RD has been identified by the CRC. If additional cumulative safety or preliminary efficacy results from dose escalation or exploration suggest that an alternate dose or schedule may improve the benefit relative to risk in treatment with FPT155, more than one dose or schedule may be evaluated in the phase 1b cohorts.

Up to 8 tumor-specific cohorts consisting of approximately 30 patients each will evaluate the safety, efficacy, PK, and PD of FPT155 at a RD (see [Appendix 11](#)). Patients with advanced RCC and melanoma who have failed prior anti-PD(L)1 therapy will be enrolled in 2 of the 8 cohorts.

Additional tumor types for the remaining Phase 1b cohorts will be determined based on emerging safety, translational, and clinical data for FPT155, as well as any potential new safety signals from other immunotherapies, such as significant changes to prescribing information for approved immunotherapies.

Intensive monitoring will occur in the outpatient setting and include a minimum 6-hour observation window following completion of the first and second infusions. Additional monitoring requirements may be implemented based on emerging safety data from Phase 1a dose escalation.

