2.1.2 FPT155 + Pembrolizumab

FPT155 will be administered Q3W over approximately 60 minutes by intravenous IV infusion

followed by 200 mg of pembrolizumab administered over 30 minutes by IV infusion a minimum of 30 minutes after the completion of FPT155. Eligible patients with advanced lung cancer will be enrolled for treatment with the combination of FPT155 and pembrolizumab.

Combination dose escalation will start with a FPT155 dose that is a minimum of two dose levels lower than the highest dose cleared in FPT155 monotherapy.

Combination dose exploration will include up to 30 patients who may be enrolled at one or more dose levels to further evaluate safety, PK, PD, and clinical activity (conditional upon the dose level clearing dose escalation criteria).

For patients enrolled for treatment with FPT155 and pembrolizumab, treatment will continue until disease progression, unacceptable toxicity or consent withdrawal. If one drug is discontinued, treatment may continue with the other alone for up to an additional 12 months.

2.1.3 Proposed FPT155 Dose Levels:

FPT155 will be initially administered Q3W, on Day 1 of each 21-day cycle. The anticipated dose levels are outlined in [Table 1](#).

Table 1 Anticipated Dose Levels

Design	Cohort*	FPT155 Dose
Accelerated titration design	1aM1	0.07 mg
	1aM2	0.21 mg
	1aM3	0.70 mg
	1aM4	2.1 mg
3+3 design	1aM5	7 mg
	1aM6	21 mg
	1aM7	42 mg
	1aM8	70 mg
	1aM9	140 mg
	1aM10	280 mg
	1aM11	560 mg
	1aM12	840 mg
	1aM13	1260 mg

* Dose escalation cohorts, for example: 1aM1= Phase 1a FPT155 Monotherapy cohort 1.

Planned dosing increments take into account conservative estimates of receptor occupancy (RO) and pharmacological activity (PA) through both Cluster of Differentiation 28 (CD28) and Cytotoxic T-lymphocyte-associated protein 4 (CTLA-4). Fixed 3-fold escalation increments are proposed while projected engagement of CD28 is low; more conservative increments (2-fold or less) are proposed at higher CD28 occupancy levels.

The Sponsor may add cohorts with alternative dose levels or dose regimens (e.g., different dosing frequency, intermediate dose levels) upon review of safety, PK, and PD profiles to achieve optimal target exposure with acceptable tolerability.

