6.1.3 Treatment Exposure and Compliance

6.1.3.1 Treatment Exposure

Descriptive statistics will be provided by treatment for the following

- Number of FPT155 Administered
- Cumulative dose (mg)
- Total duration of exposure to study drug (weeks)

Total duration of exposure to study drug (in weeks) will be defined as (last available dosing date – first dosing date + 21)/7, regardless of any temporary interruptions in study drug administration.

The number and percentage of subjects who have dose reduction, dose delay or interruption, and infusion interruption will be summarized with reasons.

Summaries of exposure will be performed with the safety population. A by-subject listing of study drug administration will be provided.

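### If a non-Q3W Phase 1a cohort opens at a cleared dose level, the SAP's combining rule read literally merges it with Q3W patients, and the exposure formula is one week too long for each Q2W patient

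*SAP*

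**What the plan says.** **What may be given.** The base regimen is every three weeks: "FPT155 will be initially administered Q3W, on Day 1 of each 21-day cycle" (SAP 2.1.3). Both documents leave room for another interval. Protocol 4.1.1.2, in the text after Table 5, says that once a dose has cleared on Q3W, "more frequent (eg Q2W) dosing at the same dose level may be evaluated using the 3+3 framework". SAP 2.1.3 says: "The Sponsor may add cohorts with alternative dose levels or dose regimens (e.g., different dosing frequency, intermediate dose levels"). Protocol 6.5 describes assignment in dose exploration as being to a dose level and a schedule together.

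**How patients are grouped.** SAP 5.1 opens with "Subjects will be grouped according to the actual treatment they received". Its next sentence is the only explicit combining rule: "Subjects with the same dose level from the dose escalation and exploratory in Phase 1a for monotherapy", together with the Phase 1a combination patients on the same basis, are to be combined for summary. Treatment is not defined there or elsewhere in the SAP as dose plus schedule. SAP Table 1 lists design, cohort and dose, without the regimen column that protocol Table 5 carries.

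**PK.** SAP 6.4.1 tabulates and plots concentrations and summarises parameters by dose level.

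**Exposure.** SAP 6.1.3.1 defines duration in weeks as ("last available dosing date – first dosing date + 21)/7, regardless of any temporary interruptions in study drug administration". The 21 is the same for every patient.

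**The concern.** The grouping key distinguishes milligrams per dose but not the interval between doses. Two Phase 1a cohorts on the same milligrams at different frequencies would share a key, and a programmer following the combining sentence as written would report them as one group. A difference in toxicity or exposure between schedules would then be averaged within one column of the tables.

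PK is affected where the result depends on the interval. The protocol defines the trough at the end of each dose interval, so a pooled trough would mix day 14 with day 21 values, and multiple-dose summaries would mix different accumulation.

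The exposure formula is a separate problem. It is right for Q3W and wrong for any other interval, whatever is decided about grouping.

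**Working it through.** **Inputs.** Base interval 21 days (SAP 2.1.3). Q2W interval 14 days (the protocol 4.1.1.2 example). Constant of 21 days (SAP 6.1.3.1). Dose levels 560 and 840 mg and 1.5-fold steps above 560 mg (protocol 4.1.1.2 and 4.6). DLT window 21 days (protocol 4.1.1.3). Predicted half-life under 10 days (protocol 4.6). All results assume no delays or reductions.

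**1. The plan's formula on its own schedule.** For n on-schedule Q3W doses, the last dose falls 21(n − 1) days after the first. Duration = (21(n − 1) + 21)/7 = 3n weeks, so n = 1, 2, 3, 6 gives 3, 6, 9, 18 weeks. The 21 is therefore exactly one Q3W interval.

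**2. The same formula on Q2W.** SAP: (14(n − 1) + 21)/7 = 2n + 1 weeks. With the assigned interval: (14(n − 1) + 14)/7 = 2n weeks.

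| Q2W doses | SAP formula (weeks) | Assigned interval (weeks) | Excess |
|---|---|---|---|
| 1 | 3 | 2 | 50% |
| 2 | 5 | 4 | 25% |
| 3 | 7 | 6 | 16.7% |
| 6 | 13 | 12 | 8.3% |

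The error is always one week, a shrinking share as doses accumulate. Dividing cumulative dose by the SAP duration gives an apparent Q2W/Q3W ratio of 3n/(2n + 1), which is 1.00, 1.20, 1.29 and 1.38 at n = 1, 2, 3 and 6, against a planned 1.50.

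**3. Planned dose per week at equal milligrams.** Ratio 21/14 = 1.5. At 560 mg, Q3W is 560/3 = 186.7 mg/week and Q2W is 560/2 = 280 mg/week. The latter equals 840/3 = 280 mg/week, the weekly rate of the next escalation level on Q3W. The equality concerns average weekly dose, not the concentration profile.

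**4. Doses within the DLT window.** Q2W: days 1 and 15, two doses. Q3W: day 1, one dose.

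**5. Effect on a pooled 560 mg group.** The documents give no Q2W numbers, so take assumed shares of 10%, 25% and 50%. Mean planned rate = (1 − share) × 186.7 + share × 280 = 196.0, 210.0 and 233.3 mg/week, which is 5%, 12.5% and 25% above Q3W alone.

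**6. Trough.** Assuming log-linear decline and a 10-day half-life, the upper end of the protocol's prediction, the first-interval trough at day 14 is 2^(7/10) = 1.6 times that at day 21. A shorter half-life widens the gap. Before any second dose, patients on either schedule have had identical dosing, so first-dose peak and concentrations at matching times can properly be pooled.

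**7. Whether another output would show the difference.** Compliance and dose intensity (SAP 6.1.3.2) are taken relative to each patient's own plan, so both read about 100% on either schedule. Number of administrations and cumulative dose are reported separately and are correct, but neither carries the interval.

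**The case against.** The strongest reply is that "Subjects will be grouped according to the actual treatment they received" governs. On that view, the same milligrams at two frequencies are two treatments, and the next sentence merely joins escalation with exploration. Many SAP outputs are specified by treatment or treatment group, and protocol 9.0 foresees presentation by cohort. That reading is possible, and it is why the point is an ambiguity rather than a certain merger. It does not settle the matter, because treatment is undefined and the one explicit rule uses dose level alone.

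Second, the case is hypothetical. Every level in protocol Table 5 is Q3W, Appendix 11 endorses 560 mg Q3W, and no document shows a Q2W cohort opening. This stands. The SAP is also to be finalised before database lock, when any added schedule would be known. In an open-label study, however, leaving the grouping until then means choosing it with results in view.

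Third, PK parameter calculation is sent to a separate plan that is not available here, and SAP 6.4.1 qualifies its parameter tables as applying where appropriate. That softens the PK part, but the only grouping variable stated remains dose level.

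Two stronger inferences are tempting and unsupported:

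- **Phase 1b patients would be pooled across schedules by the same rule.** Protocol 4.1.3 does say "more than one dose or schedule may be evaluated in the phase 1b cohorts", but the SAP 5.1 combining sentence covers only Phase 1a, and SAP section 5 summarises Phase 1b separately.
- **Pooled tables would mislead escalation or the choice of recommended dose.** Those decisions belong to the Cohort Review Committee, working on emerging data (protocol 4.1.1.1 and 4.1.1.6). A Q2W cohort would run within a 3+3 framework. SAP 6.3.1.7 specifies DLT tables by organ class, term and severity without stating dose-level pooling, and by-subject listings are planned.

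**Conclusion.** The point holds conditionally. If a Q2W or other non-Q3W Phase 1a cohort opens at a cleared dose level, SAP 5.1 read literally merges patients whose planned weekly dose differs 1.5-fold, a ratio equal to the step the protocol uses between dose levels above 560 mg. The sentence on actual treatment does not clearly prevent this. SAP 6.4.1 would mix trough and multiple-dose PK in the same way. Exposure would be overstated by exactly one week per on-schedule Q2W patient.

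The figures rest on planned dosing without delays and on Q2W as the example. How far any safety table would shift cannot be estimated, because the documents give no Q2W counts or event rates. The matter concerns final reporting of Phase 1a and is worth settling before the SAP is finalised. It implies no view on which schedule should be used.

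**What to change.** - **SAP 5.1:** define the Phase 1a treatment group as FPT155 dose level and assigned schedule, separately for monotherapy and combination. Combine escalation and exploration patients only when both dose level and schedule match.
- **SAP 6.4.1:** summarise trough and multiple-dose PK by dose level and schedule. First-dose data collected before the second dose may be pooled by dose level at matching times.
- **SAP 6.1.3.1:** replace 21 with the patient's assigned dosing interval in days.

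The cost is a sentence or two in each of three SAP sections, plus a schedule variable in the analysis datasets. No protocol amendment or extra data collection is needed, and no output changes if every patient stays on Q3W.

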5.2 Handling Dropouts and Missing Values

In general, missing data will not be imputed unless methods for handling missing data are specified.

The following imputation rules will be used to impute start date and stop date of adverse event and concomitant medication.

- For stop date: If the month and year are present, impute the last day of the month. If only the year is present, impute December 31 of that year. If the stop date is entirely missing, assume the event or medication is ongoing. If a partial or complete stop date is present and the 'ongoing' or 'continuing' box is checked, then it will be assumed that the adverse event or concomitant medication stopped and the stop date will be imputed, if partial. If imputed stop date is after end of study (EOS)/Death date then EOS/Death date will be used as stop date.
- For start date: please refer to [Table 8](#) below.

Table 8 Imputation Rules for Start Date of Adverse Event and Concomitant Medication.

Missing	Imputation	Exception
Day	01	Default to Study Day 1 if an adverse event starts the same year and month as Study Day 1 and the flag indicates that the adverse event started on or after the first dose on the Adverse Events eCRF
Day/Month	01 JAN	Default to Study Day 1 if an adverse event started the same year as Study Day 1 and the flag indicates that the adverse event started on or after the first dose on the Adverse Events eCRF
Day/Month/Year	If complete stop date present Stop date < first dosing date: Impute January 1 of the stop year Stop date \geq first dosing date: Impute the date of first dose If partial stop date present ie, YYYYMM Partial Stop date < first dosing date: Impute January 1 of the stop year Partial Stop date \geq first dosing date: Impute the date of first dose If partial stop date present ie, YYYY	

Partial Stop date < first dosing date: Impute January 1 of the stop year Partial Stop date \geq first dosing date: Impute the date of first dose If stop date is completely missing: Impute the date of first dose	
-------------------------------------------------------------------------------------------------------------------------------------------------------------------------------------------------------------------------------------	--

Date of disease diagnosis, prior anti-cancer therapy and new anticancer therapy will be imputed using the same rule when only the date is missing (no imputation when month or year is missing).

The following imputation rules in will be used for partial or missing death dates.

- If death year and month are available but day is missing:
 - If yyyymm for the date last known to be alive equals yyyymm for death date, set death date to the day after the date last known to be alive.
 - If yyyymm for the date last known to be alive is less than the yyyymm for death date, set death date to the first day of the death month.
 - If yyyymm for the date last known to be alive is greater than yyyymm for death date, assume death date is in error, do not impute and censor the subject survival time.
- If month and day are missing and year of death is known:
 - If yyyy for the date last known to be alive equals yyyy for death date, set death date to the day after last known to be alive date.
 - If yyyy for the date last known to be alive is less than yyyy for death date, set death date to the first day of the death year.
 - If yyyy for the date last known to be alive is greater than yyyy for death date, assume death date is in error, do not impute and censor the subject survival time.
- If a death date is totally missing:
 - Set death date to the day after the date last known to be alive. If the date last known to be alive is a partial date, set it to the first day of the month last known to be alive or first day of the year last known to be alive if month is also missing.

Outliers will be identified during the data management and data analysis process, but no sensitivity analyses will be conducted. All data will be included in the data analysis.

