### 8.1 Efficacy Assessments

#### 8.1.1 Tumor Assessment for the Study

Tumor assessments consist of clinical examination and appropriate imaging techniques (preferably CT scans with appropriate slice thickness per RECIST v 1.1; MRI is acceptable). Assessments should be performed as outlined in the Schedule of Assessments. The same methods used to detect lesions at baseline are to be used to follow the same lesions throughout the clinical study.

Tumor response assessment will be performed by the investigator per RECIST v 1.1 guidelines ([Eisenhauer 2009](#)).

Tumor assessments will be performed at screening, then every 6 weeks from the first dose for 24 weeks, and then every 12 weeks thereafter. Once an initial CR or PR is reported by the investigator, confirmatory scans must be performed 4–6 weeks later.

If patient terminates study treatment prior to scheduled CT/MRI scans, patient should have scans done at the EOT visits (does not need to be repeated if performed within 8 weeks prior to the end of treatment visits, or if tumor progression was previously determined).

After discontinuation of study treatment for reasons other than progressive disease, withdrawal of consent, or initiation of additional anti-cancer therapy, tumor assessments will continue every 12 weeks until disease progression, withdrawal of consent or start of new anti-cancer therapy.

In the Phase 1b portion of the study, patients in LTFU for survival must have tumor scans every 12 weeks if tumor progression was not previously determined and/or use of alternative anti-cancer therapy has not been initiated.

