6.2.3 Efficacy Endpoint: DOR

Duration of Response (DOR) is defined as the time from first response (CR or PR determined by the investigator per RECIST v1.1) that is subsequently confirmed until the onset of progressive disease or death from any cause, whichever comes first.

DOR in months will be calculated as: (date of first progression or death from any cause – date of first confirmed CR or PR + 1)/30.4375. Patients who are alive and progression-free at the time of data analysis will be censored at the time of their last assessment for tumor response. DOR for CR and PR patients will be summarized using 25th, 50th (median), and 75th percentiles with associated 2-sided 90% CIs, as well as percentage of censored observations. The median will be estimated by using the Kaplan-Meier method and corresponding 2-sided 90% CI using Brookmeyer and Crowley methodology (using log-log transformation). The detailed censoring rules are displayed in [Table 10](#).

Table 10 Censoring Rules for DOR

Situation	Outcome	Date of Progression or Censoring	Event Description/ Censoring Reason
No baseline tumor assessments	Censored	Date of first dose	No baseline tumor assessment
No baseline tumor assessment, but death within two consecutive tumor assessments period after first dose	Censored	First tumor assessment date	No baseline tumor assessment
No post-baseline tumor assessments and no death	Censored	Date of first dose	No post-baseline tumor assessment

No post-baseline tumor assessment and death after two or more consecutive missing tumor assessments from first dose	Censored	Date of first dose	No post-baseline tumor assessment
Disease progression before receiving subsequent anticancer therapy or data cutoff, whichever happens first	Event	Date of first documented progression per RECIST v1.1 (excludes clinical progression)	PD
Death without documented PD and not receiving new anticancer therapy on or before data cutoff	Event	Date of death	Death
Disease progression or death after two or more consecutive missing tumor assessments	Censored	Date of last evaluable tumor assessment prior to disease progression or death	Two or more consecutive missing tumor assessments
Subsequent anticancer therapy received without documented PD or death prior or on the same day	Censored	Date of last evaluable tumor assessment prior to the date of initiation of subsequent anticancer therapy	Started new anti-myeloma treatment before PD or death.

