6.2.4 Efficacy Endpoint: PFS

Progression Free Survival (PFS) defined as time from the first dose of study treatment until the first documentation by the investigator of disease progression per RECIST v1.1 or death from any cause, whichever comes first.

PFS in months will be calculated as: (date of first progression or death from any cause - date of first dose + 1)/30.4375. Patients who are alive and progression-free at the time of data analysis will be censored at the time of their last assessment for tumor response. PFS will be summarized using 25th, 50th (median), and 75th percentiles with associated 2-sided 90% CIs, as well as percentage of censored observations. The median will be estimated by using the Kaplan-Meier method and corresponding 2-sided 90% CI using Brookmeyer and Crowley methodology (using log-log transformation). The same censoring rules as DOR will be applied. See details in [Table 10](#).

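### A new anticancer therapy date with a missing day is set to the 1st of the month, so a progression documented in that month can be censored in PFS and DOR

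*SAP*

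**What the plan says.** SAP 5.2 (Handling Dropouts and Missing Values) covers partial dates for new anticancer therapy in one sentence: "Date of disease diagnosis, prior anti-cancer therapy and new anticancer therapy will be imputed using the same rule when only the date is missing", with the bracket "no imputation when month or year is missing". The bracket shows that only the day is ever imputed. The rule for a start date is Table 8: a missing day becomes 01. The one exception in that row moves the date to Study Day 1, and only for adverse events flagged on the eCRF as starting on or after first dose.

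Table 10 (SAP 6.2.3) uses the therapy date in two rows. Progression is an event under "Disease progression before receiving subsequent anticancer therapy or data cutoff, whichever happens first". A patient is censored under "Subsequent anticancer therapy received without documented PD or death prior or on the same day", at the last evaluable tumor assessment before therapy began. SAP 6.2.4 carries the table over to PFS: "The same censoring rules as DOR will be applied". PFS percentiles will be reported "as well as percentage of censored observations"; DOR has the same output.

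Partial death dates are handled differently in the same section. If the month of death is also the month the patient was last known alive, the instruction is to "set death date to the day after the date last known to be alive". That is a floor at a known date. New therapy dates have none.

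**The concern.** Day 01 is the earliest date the therapy could have started. If progression was documented on the 10th and the new drug began later that month on an unrecorded day, the imputed start falls nine days before the progression. Table 10 then treats the patient as having switched without progressing, and a failure the site documented becomes a censored observation.

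Progression before new therapy is the expected order. Off treatment, Protocol 8.1.1 says "tumor assessments will continue every 12 weeks until disease progression, withdrawal of consent or start of new anti-cancer therapy", so a documented progression will usually have come first. Only patients who progressed can be affected, so the censoring is tied to the outcome and biases Kaplan-Meier PFS and DOR upward in expectation. Both are secondary efficacy endpoints in Phase 1b, in cohorts of about 30.

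Table 10 also has a wording gap. For progression on the same day as new therapy, the censoring row excludes the patient, but the event row says only before. No row clearly classifies that patient.

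**Working it through.** The plan states no figure for this point, so there is none to reproduce. The check applies the rules to dates and then sizes the effect under labelled assumptions.

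**1. Worked dates.** The SAP formula is (end date − first dose + 1)/30.4375. First dose is 4 Jan 2021, with scans every 6 weeks on 15 Feb, 29 Mar and 10 May.

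| Progression | Therapy recorded | Imputed | SAP as written | With floor at progression |
|---|---|---|---|---|
| 10 May | day unknown, May (true 17 May) | 1 May | censored 29 Mar, 85/30.4375 = 2.79 months | event, 127/30.4375 = 4.17 months |
| 15 Feb | day unknown, Feb (true 22 Feb) | 1 Feb | censored at first dose, 1/30.4375 = 0.03 months | event, 43/30.4375 = 1.41 months |
| 29 Mar | day unknown, Apr (true 5 Apr) | 1 Apr | event, 2.79 months | event, 2.79 months |

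The flip needs a missing day, progression and therapy in the same month, and progression on day 2 or later.

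**2. Chance of a flip, given a missing day.** For a true gap of g days from progression to therapy, counted over every day of a 4-year calendar, the probability is close to 1 − (g + 1) × 48/1461 (48 months in 1,461 days).

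- g = 7: 0.74; g = 14: 0.51; g = 21: 0.28; g = 28: 0.05.
- Means over gap ranges: 0.392 (7–28 days), 0.491 (1–28), 0.144 (14–42), 0.0046 (28–42).

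**3. Share of documented progressions lost.** This is share starting therapy × share of days missing × mean flip probability. The 60% share, the gaps and the missing-day rates are assumptions.

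- 7–28 days, 5% missing: 0.6 × 0.05 × 0.392 = 1.18%.
- 7–28 days, 10% missing: 0.6 × 0.10 × 0.392 = 2.35%.
- 14–42 days, 10% missing: 0.6 × 0.10 × 0.144 = 0.9%.
- 1–28 days, 10% missing: 0.6 × 0.10 × 0.491 = 2.9%.
- Half of patients treated beyond progression (Protocol 4.3, taken as a 28–42 day gap): 0.6% at 5% missing and 1.2% at 10%. All treated beyond progression: under 0.1%.
- Stress case, 7–28 days, 30% missing: 0.6 × 0.30 × 0.392 = 7.1%.

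**4. Patients per 30-patient cohort**, assuming 18–24 documented progressions. At 5% missing: 18 × 0.0118 = 0.2 to 24 × 0.0118 = 0.3. At 10%: 18 × 0.0235 = 0.4 to 24 × 0.0235 = 0.6. At 10%, the chance that a cohort has no affected patient is 0.9765^18 = 0.65 to 0.9765^24 = 0.56.

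**5. Effect on the planned outputs.** This is a simulation of 400,000 patients: exponential PFS with median 4.6 months, 20% of events deaths without progression, the protocol scan schedule, and cutoff 6–18 months after first dose.

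- Percent censored: 22.2% with no loss, 23.0% at 5% missing, 23.7% at 10%, 26.5% at 30%.
- Kaplan-Meier median: 5.39 months with no loss, 5.42 at 10%, 5.49 at 30%.
- In simulated 30-patient cohorts the median is unchanged in 88–89% at 5% missing and 77–79% at 10%. The mean shift is about 1.2 and 2.8 days.
- With an assumed median of 2.5 months, percent censored goes from 7.6% to 8.5% (5%) and 9.3% (10%), and the large-sample median stays at 2.92 months.

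**The case against.** The strongest objection is size. The shift in median PFS is a few days at most under the central assumptions, against scans 6 and then 12 weeks apart, in an estimation trial with no hypothesis. Every driving input is assumed. Protocol 4.3 allows treatment beyond progression in all cohorts, which shrinks the effect. Protocol 10.6 has sites queried about missing data. For DOR the effect is smaller still: with 6 responders, 61.5% with documented progression (the simulated share) and 10% of days missing, 6 × 0.615 × 0.0235 = 0.09 patients. Protocol 2.3 reports only one unconfirmed partial response so far. All of this stands and keeps the point at low priority.

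SAP 6.2.5 already plans by-subject listings of tumor response, subsequent therapy and the efficacy endpoints, so affected patients could be found. That is true, but a listing does not change how the patient is analysed.

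Protocol 8.1.1 also asks for scans at the end-of-treatment visits, with no stated exemption for patients who have switched. Someone who switched on clinical progression could have RECIST progression documented later that month, and the floor would count it as an event. This is a real cost of the fix, and its frequency is not known.

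The bias is upward in expectation, not in every cohort. Earlier censoring shrinks the risk set, and the median fell in 1.5–6% of simulated cohorts. The same-day wording can sensibly be read as an event, so that part is a clarification.

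**Conclusion.** The point holds. It is a stated rule that gives a wrong classification, and it follows from the SAP text alone. A same-month documented progression is censored whenever the day of new therapy is missing, and the rule cannot err in the opposite direction. The death-date rule in the same section shows that the safeguard was available.

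The size depends on inputs the documents do not give. Under the central assumptions it is 1.2–2.4% of documented progressions, 0.8 to 1.5 percentage points more censoring, and little or no change in the median. The range across other gaps and missing-day rates runs from under 0.1% to 7.1% of progressions. PFS and DOR are descriptive, and no power figure, recommended-dose choice or decision rule is affected. It is worth correcting because it is cheap, not because it threatens a conclusion.

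**What to change.** In SAP 5.2, when only the day of new anticancer therapy is missing, impute the later of the 1st of that month and the date of any progression documented in that month, and no later than death or data cutoff. Because this can place therapy and progression on the same date, reword the Table 10 event row to cover progression before or on the same day as subsequent anticancer therapy, keeping its data-cutoff clause, so that it agrees with the censoring row. Flagging the affected patients in the planned listings, or rerunning PFS and DOR with day 01, is optional.

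The cost is one derivation rule and one row of text. The downside is that a patient who truly switched before a same-month progression is counted as an event; the flag or the day-01 run shows how many patients the choice affects.
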